4.2 Compensation

Participants will receive a maximum compensation of \$1000. This is a fair amount, in our opinion, as meals and snacks are provided to participants. Participants will thus save on groceries by participating in this study. Participants will receive \$25 for the screening visit; however, no compensation will be provided for those who only participate in the consent portion of the screening visit. Participants will receive another \$975 after they complete both dietary interventions. Participants will be paid in full at the end of the study. If a participant drops out of the study before completing all two diet intervention periods they will be paid according to the degree of completion if only one diet is completed. No compensation other than the \$25 for the screening is provided if participants drop out in the first week of the first diet intervention.

5. RISK/BENEFIT ASSESSMENT

This study provides no potential benefit to the participant other than the satisfaction of having contributed to the potential future benefit of others. Participants will be provided with their lab clinical results, which may be of interest to them. Society may benefit by having more information about how different farming practices impact the healthfulness of foods, which may help inform consumer food choices and food policy. Participation in this study may lead to increased risk for the following:

- **Blood draws:** Blood drawing can result in bruising, mild discomfort, and rarely, an infection where the needle enters the skin. There also is a possibility of lightheadedness and fainting. Sterile techniques and the use of trained phlebotomists will minimize these risks.

- **Questionnaires:** There is no known risks associated with various questionnaires (FFQ, PSQI, SF-36, PSS, POMS, MacArthur Socio-Economic Status Questionnaires, and Physical Activity Questionnaire) administered as part of this study; however, there is a possibility that participants may find some of the questions uncomfortable to answer.
- **Gastrointestinal Distress:** Minor gastrointestinal discomforts and/or distress may result from dietary changes. Dietary interventions that vary from habitual diets in fiber and macronutrients have the possibility of temporal discomfort to participants' gastrointestinal health and, in the event this occurs, the discomfort will be temporal and will subside.

6. COSTS TO THE SUBJECT

There will be no costs to participants for any of the treatments or testing done as part of this research study. Immediate necessary care is available if an individual is injured because of participation in a research project. However, there is no provision for free medical care or for monetary compensation for such injury. During this study, hospitalizations or additional care beyond the scope of this study will be the responsibility of patients and/or their insurance company.

7. ANALYTICAL PROCEDURES AND STATISTICAL CONSIDERATIONS

- **Inflammation:** Inflammatory biomarkers (IL-6, VCAM-1, TNF-alpha and C-reactive protein [CRP]) will be measured using ELISA kits at Dr. [name]'s laboratory at Utah State University. Plasma samples will be stored at -80°C until cytokine analyses are performed.
- **Dietary logs:** The Diet History Questionnaire III (NIH) and 7-day food records will be analyzed by dietetic staff within Dr. [name]'s laboratory at Utah State University.
- **Metabolomics:** Mass spectrometry techniques will be used for untargeted and/or targeted assessment of blood and/or urinary metabolites. This analysis will give insight into the appearance of food-derived metabolites in the human body and how they may impact biomarkers of human health. This analysis will be performed using de-identified samples by Metabolon Inc (a company dedicated to metabolomics analysis) and/or the Plants for Human Health Institute. Samples will be provided to these core services as de-identified samples. No other data will be shared with these core services. Plasma and urine samples will be stored at -80°C until metabolomics analyses are performed.
- **Gut microbiome taxonomy:** DNA will be extracted from stool samples using a QIAamp Fast DNA Stool Mini Kit following manufacturer's instructions and analyzed for taxonomic assignment using 16s rRNA sequencing at Utah State University's Genomics Core. Samples will be provided to the core service as de-identified samples. No other data will be shared with the core service.

- **Statistical analysis:** Change scores (post-dietary intervention – baseline) will be created for all inflammatory biomarkers and metabolites. Metabolic intermediate data will be reduced into Metabolic Factors using Principal Component Analysis (PCA) of the change scores. Factor scores will be computed for each individual for both diets. Change scores and factor (change) scores for both diets will be compared using paired t-tests. $P < 0.05$ will be considered statistically significant and analyses will be performed in SAS 9.4 (SAS, Cary, NC).
- **Power Calculations:** Using untargeted metabolomics for our power calculations of the number of participants we need to recruit, we assume a P -value ≤ 0.05 , Q -value ≤ 0.3 , and standard deviation of 0.3 based on previous work^{7,8}. 600 metabolites are typically identified and a conservative estimation in longer-term dietary intervention trials is that 40-80 metabolites will be significantly different with a mean of 0.157 (18 % difference). An $n=34$ per group is expected to provide true discovery rates ranging from 89-93 % assuming differences in 40-80 metabolites. Assuming a drop-out of 25%, the final number of participants we anticipate to recruit is $N=40$.

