4. SUBJECT RECRUITMENT AND COMPENSATION

4.1 Recruitment

Subjects will be recruited by posting flyers in designated areas around USU's campus, and through advertisement on public Facebook pages (Cache Valley Classifieds and/or Marketplace), local NextDoor pages, Craigslist, Reddit (R/Logan), Instagram, and/or Twitter. In the advertisement, potential subjects for this study will be directed to contact the study team by email or phone to obtain more information about the study, if interested. Participants who are interested will be provided with a copy of the informed consent by email. When the participant expresses interest in being in the study, the study team member will confirm, by telephone, that the participant meets most of the inclusion/exclusion criteria (ones that can be determined without the need for a blood draw) before scheduling him/her for a consent meeting. Subjects will attend a one-on-one information/consent session that will be conducted by a trained member to present the details of the study. We anticipate that we will need to telephone screen approximately 150 people and that approximately 30 will be consented. We will enroll up to 40 participants to meet our goal of having at least 18 participants complete the study.

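### Each PCA factor score is tested at P<0.05 with no adjustment across factors, so the chance of a false-positive factor is about 22-26% with 5 factors and 37-43% with 10

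*Combined protocol and SAP*

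**What the plan says.** The Statistical analysis item of Section 7 forms change scores for all inflammatory biomarkers and metabolites. It continues: "Metabolic intermediate data will be reduced into Metabolic Factors using Principal Component Analysis (PCA) of the change scores". Then: "Factor scores will be computed for each individual for both diets". The comparison follows: "Change scores and factor (change) scores for both diets will be compared using paired t-tests". The significance threshold is P<0.05, and no multiplicity rule accompanies it.

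The item does not say whether the PCA is fitted once or once per diet, how the data are scaled, how many factors are kept, or by what rule.

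Three other places set the size of the problem:

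- The Power Calculations item says "600 metabolites are typically identified". This describes untargeted metabolomics and is not given as the PCA input. A Q-value of at most 0.3 appears in the same item, as a power assumption only.
- The Metabolomics item leaves the assay open: "Mass spectrometry techniques will be used for untargeted and/or targeted assessment of blood and/or urinary metabolites".
- The Power Calculations item closes with "Assuming a drop-out of 25%, the final number of participants we anticipate to recruit is" 40, while Section 4.1 sets a "goal of having at least 18 participants complete the study".

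**The concern.** The factor scores are the plan's condensed summary of the metabolome for Objective 2. A 5% threshold applied to each of several factors does not give a 5% chance of a false claim for the set; the chance grows with the number of factors kept. Because that number is open, the size of the error is open too, and the number could be settled after results are seen.

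The unstated way of fitting matters as well. Centred PCA scores average zero over the rows used in the fit, so a separate fit per diet would remove the very difference that the t-test is meant to detect.

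**Working it through.** **Inputs.** The plan gives no error rate for the factor tests, so there is no figure of its own to reproduce. From Section 7: 40 recruited, 25% drop-out, 0.05 per test (two-sided assumed, since the plan does not say), and about 600 metabolites if the assay is untargeted.

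- Completers: 40 × (1 − 0.25) = 30.
- Rows if both diets are stacked: 2 × 30 = 60, hence at most 60 − 1 = 59 factors after centring.
- At the Section 4.1 minimum of 18 completers: 36 rows and at most 35 factors.

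**Step 1: chance of at least one false-positive factor.** For k independent tests at 0.05 the chance is 1 − 0.95^k. Factors from one PCA are not exactly independent, so the formula was checked by simulation: 30 completers, 600 metabolites, no diet effect, one PCA on the stacked rows, a paired t-test per factor.

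| Factors kept (k) | 1 − 0.95^k | Simulation |
|---|---|---|
| 1 | 5.0% | 4% |
| 3 | 14.3% | 11-17% |
| 5 | 22.6% | 22-26% |
| 10 | 40.1% | 37-43% |
| 59 (all) | 95.2% | 98-99% |

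For a fixed k the formula does not involve the number of metabolites. With Holm across the retained factors, the simulated chance was about 3-8% for 3, 5, 10 and 59 factors.

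**Step 2: if an eigenvalue-above-1 rule were used.** The plan names no rule; this one is common. With 600 standardised columns and 59 factors the mean eigenvalue is 600/59 = 10.2, so the rule removes few or none. Simulated with 30 completers and no diet effect:

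| Columns and correlation | Factors kept | Chance of at least one false positive |
|---|---|---|
| 600, independent to moderately strong | 46-59 | 0.89-0.99 |
| 600, very strong (communality 0.9-0.95) | 20-34 | 0.68-0.89 |
| 150 | 29-46 | 0.78-0.94 |
| 60 | 12-23 | 0.48-0.71 |
| 30 | 8-13 | 0.34-0.49 |
| 15 | about 7 | 0.27-0.30 |

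With 18 completers and 600 independent columns the figure is 0.89. Keeping enough factors for 80% of the variance (about 28, with 30 completers) gives 0.75.

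**Step 3: if a PCA were fitted to each diet.** Let a_ik and b_ik be the scores of person i on factor k under the two diets. Centring makes the mean of a_ik and the mean of b_ik both zero. The mean paired difference is then 0 − 0 = 0, and so is t, whatever the diets do. A numerical check with a true shift of 0.5 SD in all 600 metabolites gave a largest mean difference of 2 × 10⁻¹⁵, which is rounding error.

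**Step 4: the number of factors also drives power.** Take the plan's 0.157 difference in 40-80 metabolites and its SD of 0.3 as the SD of the paired difference (so 0.3/√2 = 0.212 per diet), with half the noise shared over 5 factors. Bonferroni-adjusted power was 12-15% with 5 factors kept and 100% with 10. The five leading factors describe the shared noise, and the diet signal lies behind them. Choosing the number by parallel analysis kept those noise factors: the diet effect was detected in only 5-31% of trials when noise was shared over 1 or 5 factors. Holm with 10 or 20 factors fixed in advance reached 100% in the same settings.

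**The case against.** The strongest reply is that the plan contains neither an eigenvalue rule nor a per-diet fit, and that the 600 metabolites belong to the power statement. The PCA takes what the plan calls metabolic intermediate data, which could be a small targeted panel. A pooled PCA with a few factors fits the text as well as anything, and its error rate is ordinary uncorrected multiplicity. The plan also tests individual metabolite change scores, so the factors are not its only look at the metabolome.

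Much of this stands, and it rules out two stronger conclusions that a reader might draw.

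- *That the factor analysis is almost certain to give a false positive.* This needs both about 600 columns and a rule that keeps nearly every factor. The plan states neither, and the figure falls to 0.27-0.71 for panels of 15-60 metabolites even under the eigenvalue rule.
- *That the factor comparison is identically null as written.* Scores for each person under both diets, compared in pairs, are most naturally read as coming from one common set of factors. A run of t-values all equal to zero would also be noticed. The per-diet fit is permitted by silence, not prescribed.

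What the reply does not remove is the stated rule itself: P<0.05 for each test, with no adjustment across factors. The Q-value of 0.3 does not supply one, because it is only a power assumption. Inflation is absent only if a single factor is kept.

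**Conclusion.** The concern holds for the unadjusted factor tests. With 30 completers and no diet effect, the chance of at least one false-positive factor is about 11-17% with 3 factors, 22-26% with 5 and 37-43% with 10, against a nominal 5%. These figures assume two-sided tests and one PCA on the stacked change scores.

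The range of about 70-99% applies only under two conditions that the plan does not state: some 600 metabolites entering the PCA and an eigenvalue-above-1 rule. Where it falls in that range depends on the correlation among metabolites. The exact zero under a per-diet fit is certain algebra for any centred PCA, but it is a reading to close off, not the plan's stated method. Left alone, the silence on pooling and on the number of factors would be missing detail; it matters because it sets the size of the error and of the power. The point should be corrected before diet codes are attached.

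**What to change.** In the Statistical analysis item of Section 7:

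1. State that one PCA is fitted to the stacked change scores of both diets, and name the metabolites that enter and the scaling.
2. Fix the number of retained factors before diet codes are attached. The stacked fit does not need the codes. Check the chosen number by simulation over a range of correlation structures, as in Step 4.
3. Replace P<0.05 for each factor with Holm across the retained factors.

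Parallel analysis should not be prescribed for item 2, because it can drop the factor that carries the diet effect. A paired sign-flip test over all metabolites could be added as an optional supplement, but should not replace the planned analysis: its power was 37-93% in the setting of Step 4 and would need its own check.

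The cost is a few sentences of plan wording and a short simulation. The downside is a stricter threshold for individual factors: with 10 factors, the smallest P-value must be at or below 0.05/10 = 0.005.

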3. DESIGN AND PROCEDURES

3.1 Study duration

Total involvement for each participant will be 16 weeks. Each diet will be followed for 44 days (4 day rotating menus x 11 periods) with a 14-day washout period in between.

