3.3 Study Schedule

ACTIVITY/VISIT	WEEK	DURATION
PHONE SCREEN A scripted phone screen will be performed to determine pre-eligibility prior to consent.	1	15 min
CONSENT A one-on-one consent visit will be conducted privately with staff either in-person or via Zoom.	1	1 h
SCREENING This visit will take place in the morning after an overnight fast and will have the following procedures: informed consent, screening blood draw (including serum pregnancy test for women of child-bearing potential), health history, height and weight, and screening questionnaires regarding food intake, health, and sleep.	1	2 h
BASELINE VISIT DIET 1 This visit will take place in the morning after an overnight fast. Participants will be asked to complete a fasted blood draw and questionnaires, and bring in urine and stool samples that were collected using at-home collection kits.	2	1 h
INTERVENTION DIET 1 Participants will be randomized to consume one of the following sourced diets: agroecological or conventional. They will follow this nutrition pattern for 44 days. During this time, participants will come to the NDFS building twice a week to pick up food.	2-8	1 h per week
POST VISIT DIET 1 On the last day of diet 1, participants will be asked to complete a fasted blood draw and questionnaires, and bring in urine and stool samples that were collected using at-home collection kits.	8	1 h
WASHOUT PERIOD Participants will consume self-selected (habitual) diets for 14 days. No involvement from research team.	9-10	none
BASELINE VISIT DIET 2 This visit will take place in the morning and will have a fasted blood draw. Participants are also asked to bring in stool and urine samples that were collected using at-home collection kits.	10	1 h
INTERVENTION DIET 2 Participants will now start their second nutritional intervention (agroecological or conventional sourced diet depending on the diet consumed during the first intervention). During this time, participants will come to the NDFS building twice a week to pick up food.	10-16	1 h per week

POST VISIT DIET 2 On the last day of diet 2, participants will be asked to complete a fasted blood draw and questionnaires, and bring in urine and stool samples that were collected using at-home collection kits.	16	1 h
---	----	-----

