3.4 Description of study visits

Participants will be asked to complete four testing visits throughout their participation in the study (pre and post visits for each of the diets) as well as complete two on-site visits per week during each of the 44-day dietary intervention periods to consume a meal and obtain a current body weight measurement. All visits will take place in clinical research space located at the Center for Human Nutrition Studies (CHNS), except for food pickup, which will take place at the NDFS building.

Phone Screen (Week 1. Duration: 15 min): Interested participants will be pre-screened by telephone, using a scripted list of questions (attached) to identify individuals that may be eligible for study entry. Suitable candidates will then be provided a REDCap survey link to complete additional screening questions that asks them further details about their health, dietary habits, and sleep habits (see inclusion/exclusion criteria). Only the minimum PHI will be collected to determine eligibility. Responses will be reviewed by a study team member (all study team members will have completed the necessary CITI training) and potentially eligible candidates will be contacted to schedule a consent/screening visit. The pre-screen is put in place to confirm that the participant meets most of the inclusion/exclusion criteria before the subject is scheduled for a consent meeting. The phone screen is thus performed to limit the amount of ineligible research participants that are consented/screened that could easily be excluded by means of a phone screening. This would also provide interested participants with the opportunity to ask additional questions about the study and to determine if they are interested in moving forward with a consent/screening visit. This will limit both subject and research staff time burden.

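### Paired t-tests on change scores subtract both baselines at full weight and omit period; a crossover ANCOVA on the same four visits would usually estimate the diet effect more precisely

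*Combined protocol and SAP*

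**What the plan says.** The diet comparison is set out in one paragraph of section 7. First, "Change scores (post-dietary intervention – baseline) will be created for all inflammatory biomarkers and metabolites". For the metabolite factors, "Metabolic intermediate data will be reduced into Metabolic Factors using Principal Component Analysis (PCA) of the change scores". Then "Change scores and factor (change) scores for both diets will be compared using paired t-tests". No period, sequence or baseline-covariate term appears there or elsewhere.

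The design is a two-period crossover. Section 3.1 states: "Each diet will be followed for 44 days (4 day rotating menus x 11 periods) with a 14-day washout period in between". Section 3.4 provides "four testing visits throughout their participation in the study (pre and post visits for each of the diets"), and its visit descriptions have blood drawn for cytokines and metabolites at all four. Before the second baseline, section 3.3 says: "Participants will consume self-selected (habitual) diets for 14 days". Section 3.4 randomises the starting diet without giving an allocation ratio or method.

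The power paragraph in section 7 assumes "40-80 metabolites will be significantly different with a mean of 0.157 (18 % difference") and a "standard deviation of 0.3 based on previous work". It does not say whether that SD refers to a single value, a change, or a paired difference.

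**The concern.** Write A for the agroecological and B for the conventional diet. The quantity tested is (post A − baseline A) − (post B − baseline B). Each participant already serves as their own control through post A − post B. The two baselines bring in two more noisy measurements at a fixed weight of 1, which is the right weight only if baseline differences carry through to post differences almost completely. ANCOVA estimates the weight from the data.

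The test also ignores period. A shift that affects post 2 but not baseline 2 goes into the residual variance when sequences are balanced, and into the diet estimate when they are not. A shift common to baseline 2 and post 2 cancels.

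At stake is precision for each marker and metabolite. It matters more if completers fall from the 34 in the power paragraph towards the minimum of 18 in section 4.1.

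**Working it through.** **The plan's own figures.** The plan gives none for the precision of change scores or of ANCOVA. Its sample-size statement (34 per group, true discovery rate 89–93%) was not reproduced on a two-sided reading with 0.157: paired power at the Q-value limit is 74–84%. An unstated one-sided reading with ln(1.18) comes close, at 88.5–93.4%. That is a separate matter and does not affect what follows.

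**Variance ratio.** Let dY be the A−B post difference and dB the A−B baseline difference, each with variance V. Let b be the slope of dY on dB. With within-period correlation rw and between-period correlation rb, b = (rw − rb)/(1 − rb). It is not the ordinary pre–post correlation: if all four visits correlate equally, b = 0 however high that correlation is.

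- Planned contrast: Var(dY − dB) = 2V(1 − b).
- ANCOVA residual variance: V(1 − b²).
- Ratio: 2(1 − b)/(1 − b²) = 2/(1 + b).
- Estimating the slope and a period term with balanced sequences multiplies the ratio by (n − 4)/(n − 3).

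| b | large sample | n=34 | n=30 | n=18 |
|---|---|---|---|---|
| 0 | 2.00 | 1.94 | 1.93 | 1.87 |
| 0.3 | 1.54 | 1.49 | 1.48 | 1.44 |
| 0.5 | 1.33 | 1.29 | 1.28 | 1.24 |
| 0.7 | 1.18 | 1.14 | 1.13 | 1.10 |
| 0.9 | 1.05 | 1.02 | 1.01 | 0.98 |

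Here n=30 is 40 × 0.75, from the planned recruitment and drop-out. Simulation with normal data agreed to within about 0.02. ANCOVA stops gaining at b = 0.94, 0.93 and 0.87 (n=34, 30, 18) by variance. By confidence-interval width, which also counts the two lost degrees of freedom, the limits are 0.93, 0.91 and 0.83.

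**Unequal variances.** With k = Var(dB)/Var(dY), the large-sample ratio is (1 + k − 2bk)/(1 − b²k). For k from 0.5 to 1.5 at n=30, the realised ratio is 1.10 to 1.54 at b=0.5 and 1.02 to 1.45 at b=0.7. At n=18, b=0.7 and k=0.5 it is 0.99.

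**Where b may lie.** The visits fall at about days 0, 44, 58 and 102, so b = [2r(44) − r(14) − r(102)]/[2(1 − r(58))]. If correlation decays as r(t) = exp(−t/τ) (an assumption), b runs from −0.15 (τ about 18 days) to 28/116 = 0.24 (τ large), and the large-sample ratio from 2.35 to 1.61. If instead people drift along steady personal trends, b approaches 1 and the gain vanishes.

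**Power for one marker** (effect 0.157, two-sided 0.05, planned vs ANCOVA). If 0.3 is the single-visit within-person SD, V = 2 × 0.09 = 0.18. For n=30, b=0.5:

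- Planned variance 2 × 0.18 × 0.5/30 = 0.0060, SE 0.0775, noncentrality 2.03, power 50%.
- ANCOVA variance 0.18 × 0.75/30 × 27/26 = 0.0047, SE 0.068, noncentrality about 2.3, power 60%.

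| 0.3 read as | n | b=0 | b=0.5 | b=0.7 | b=0.9 |
|---|---|---|---|---|---|
| single-visit within-person SD | 34 | 32 vs 54% | 55 vs 66% | 77 vs 82% | 99.7% both |
| | 30 | 28 vs 48% | 50 vs 60% | 72 vs 77% | 99% both |
| | 18 | 18 vs 30% | 32 vs 38% | 48 vs 51% | 91 vs 90% |
| SD of paired change difference | 30 | 79 vs 97% | 79 vs 88% | 79 vs 84% | 79% both |
| | 18 | 55 vs 81% | 55 vs 64% | 55 vs 59% | 55 vs 54% |

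**Period.** The bias of the planned estimate is the post-2-only effect × (nBA − nAB)/n. An effect of 0.3 (assumed and large: one within-person SD) at n=30 gives:

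- 15/15: no bias, but power 21 vs 48% at b=0.
- 18/12: bias 0.3 × 6/30 = 0.06 in size, planned type I error still about 5%.
- 20/10: bias 0.3 × 10/30 = 0.10 in size, planned type I error about 10% (b=0) and 13% (b=0.5), against about 5% for ANCOVA.

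An effect of 0.1 at 20/10 gives about 5.6% (b=0). Under simple randomisation of 30, a split of 18/12 or worse has probability 36%, and 20/10 or worse 10%. Averaged over such splits, the planned test stays at 5.0–5.1%.

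**The case against.** **The planned test is valid.** It is simple and prespecified, and its change scores match objectives framed as before and after each diet. With balanced sequences and no differential carry-over it estimates the right quantity. This stands, and it is why the point is an improvement and not a defect.

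**The size of the gain depends on an unknown b.** The case for a low b assumes exponentially decaying correlation and ignores that adjacent visits also switch between self-selected and provided food. Personal drift would remove the gain. This stands as a limit on size. Even so, the loss at high b is about one power point at n=18, against gains of 10 to 20 points at n=30 for b of 0.5 or less on the first SD reading.

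**Carry-over can favour change scores.** Suppose half the diet-1 effect remains after washout (h = 0.157/2 = 0.0785). If it persists to post 2, change scores average 0.157, while ANCOVA averages 0.157 − (1 − b)h/2: 0.118 at b=0 and 0.137 at b=0.5. Power is then 28 vs 30% and 50 vs 49%. If the residue has gone by post 2, change scores average 0.157 + h/2 = 0.196, against 0.157 for ANCOVA at b=0. The documents cannot say which applies. This stands.

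**Period bias needs two conditions together**, a post-2-only shift and unequal sequences, and nothing in the documents points to either. This is correct, and precision is the main argument.

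**Skewed markers.** With assumed log-normal data (log SD 0.8, correlations 0.75/0.5, effect 0.5, raw-scale analysis), power at n=30 was 81 vs 83%, compared with 76 vs 85% for normal data. At b=0 the gain stayed large (56 vs 75%). The gain therefore also depends on the analysis scale, which the plan does not state.

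**Consistency.** Single metabolites would be baseline-adjusted while the PCA factors remain change scores. That is a real cost in presentation.

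**Conclusion.** The point holds as a worthwhile, inexpensive improvement. For b up to about 0.7 with equal variances, the planned contrast has 1.13 to 1.93 times the ANCOVA variance at n=30 and 1.10 to 1.87 times at n=18. There is no useful gain near b=0.9 and a slight loss above break-even. The word usually rests on assumptions about b, about equal or similar variances, and about approximately normal data. Period adjustment protects power, and protects against bias in an unbalanced realised split, but the type I error inflation shown needs a large assumed period effect. All power figures are for a single marker and are not the Q-value or true-discovery-rate criterion on which the trial was sized.

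**What to change.** For each inflammatory marker and metabolite, prespecify a complete-case regression of the A−B post difference on sequence and on the A−B baseline difference, and test the intercept as the diet effect. Code sequence exactly +1/−1 and centre neither regressor on its sample mean. With the 0.3 post-2-only effect and b=0, centring sequence gives type I error of 11% at 18/12 and 23% at 20/10; at b=0.5 and 15/15, centring the baseline difference gives 8.9%.

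A mixed model in the planned SAS 9.4 (diet, period, sequence, period baseline, participant mean baseline, random participant) gave the same diet estimate on complete data. If it is used, state the degrees-of-freedom method: the participant variance can be estimated at zero, and the standard errors then differ from the regression. State the analysis scale for skewed markers.

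For the PCA factors, keep the factor change scores and add only the period term: regress the A−B factor change difference on the same +1/−1 sequence code and test the intercept. Scoring baseline and post values on common loadings is possible but changes what the factors mean.

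Report baseline 2 by sequence descriptively, and do not present the model as a remedy for carry-over.

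The cost is SAP wording, a different SAS procedure and two degrees of freedom for the marker model (29 to 27 at n=30), with no new data. The trade-offs are little or no gain at high b, and more bias than change scores if a diet-1 residue lasts to post 2.
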